2.8 Pharmacokinetic endpoints

Not applicable

2.9 PD and PK/PD analyses

[figure not shown]
Not applicable

[figure not shown]

2.11 Biomarkers

No biomarker analyses will be included in the CSR. Separate reports will be generated if applicable.

2.13 Interim analysis

A formal interim analysis for this study is not planned and shall not be performed. For publication purposes, only descriptive data will be reported, as needed. Any decision on study continuation will not be based on these reports, as such no alpha adjustment will be needed.

The primary analysis of the study will be performed after the last subject has completed Week 26 visit or discontinued earlier. For this analysis, all subjects will have completed the assessments related to the primary, secondary [REDACTED] objectives including all variables outlined up to Week 26 and all available visit-based safety assessments. Separate SAP documentation will be prepared for this primary analysis if applicable.

3 Sample size calculation

A total of 34 evaluable subjects is required for the study to have approximately 80% power to detect at least 25% reduction in rates of priapic events (defined as an unwanted erection lasting at least 60 min reported via daily diary tool) with a mean baseline priapism event rate of 10.0 and standard deviation of the difference of 5.0, by 26 weeks.

The calculations were based on simulation with 5,000 repetitions (from Poisson distribution) using one-sample Wilcoxon's Signed-Rank Test and 2-sided $\alpha=0.05$.

Retaining the same above assumptions, robustness of the estimated sample size was also validated using a one-sample t test.

Assuming a 5% dropout rate, approximately 36 subjects will be enrolled in the study.

Recruitment of the required number of subjects with priapism will be challenging as the incidence of priapic events are sporadic and varies over time intervals. Also, in the absence of relevant clinical data on priapism, the expected reduction and higher variability in events rates have been conservatively assumed. The above expected 25% reduction in rates of priapic events from baseline is based on medical expert opinion and feedback. L-glutamine (EndariTM) was approved by the US FDA in July 2017 for the reduction of vaso-occlusive crises (VOCs), based on a 25% reduction. Since priapism is also considered to be a complicated VOC, the assumption was that the relative risk reduction of 25% (approved for VOC events), would be similar for priapism.

4 Change to protocol specified analyses

After finalization of the protocol amendment, CSEG101AUS05 Protocol Version 03, the study team noted that a few sentences which were intended to be deleted were still in the document. The changed information will be incorporated into the next version of the protocol, if amended. Team has incorporated those changes in this SAP amendment 1. These changes do not alter the purpose or intent of the amendment. The aim of this memorandum is to clarify these sentences.

Protocol amendment version 03:

- Protocol summary: Finally an analysis using a mixed effects regression model will be performed using median event counts within pre-specified time windows.
 - *The above line is proposed to be removed, as this was added in error in only this part of the protocol.*
- Section 2.6.1: Secondary efficacy endpoints will be analyzed on all FAS subjects who have completed 52 weeks on treatment to evaluate clinical efficacy of crizanlizumab 5 mg/kg.

- *Secondary efficacy endpoints will be analyzed on all FAS subjects who have completed 26 and 52 weeks on treatment to evaluate clinical efficacy of crizanlizumab 5 mg/kg.*
- Section 12.4.2: Percent reduction from baseline in priapic events will be tested using a nonparametric test (i.e. Wilcoxon's Sign Rank test). Hodges-Lehmann estimate of median percent reduction in priapic events will also be reported, along with corresponding 95% confidence intervals. The significance of the efficacy endpoints will be assessed at $\alpha = 0.05$ level.
 - *Percent reduction from baseline in priapic events will be tested using a nonparametric test (i.e. Wilcoxon's Sign Rank test) with $\alpha = 0.05$.*
Hodges-Lehmann estimate of median percent reduction in priapic events will also be reported, along with corresponding 95% confidence intervals.
- Section 12.4.4: Additionally, as the study is ongoing during COVID 19 pandemic, the impact of COVID-19 (if any) on the primary endpoint will be assessed in accordance to FDA's guideline entitled "Statistical Considerations for Clinical Trials During the COVID-19 Public Health Emergency". The analysis (as stated below) will be repeated on the FAS excluding the subjects with missing data due to COVID-19.
 - Percent reduction from baseline in priapic events will be tested using a nonparametric test (i.e., Wilcoxon's Sign Rank test). Hodges-Lehmann estimate of median percent reduction in priapic events will also be reported, along with corresponding 95% confidence intervals. The significance of the efficacy endpoints will be assessed at $\alpha = 0.05$ level.
- *Additionally, as the study is ongoing during COVID 19 pandemic, the impact of COVID-19 (if any) on the primary endpoint will be assessed in accordance to FDA's guideline entitled "Statistical Considerations for Clinical Trials During the COVID-19 Public Health Emergency". The analysis (as stated below) will be repeated on the FAS excluding the subjects with missing data due to COVID-19.*
- *Percent reduction from baseline in priapic events will be tested using a nonparametric test (i.e. Wilcoxon's Sign Rank test). Hodges-Lehmann estimate of median percent reduction in priapic events will also be reported, along with corresponding 95% confidence intervals.*
 - *Percent reduction from baseline in priapic events will be tested using a nonparametric test (i.e. Wilcoxon's Sign Rank test) with $\alpha = 0.05$.*
Hodges-Lehmann estimate of median percent reduction in priapic events will also be reported, along with corresponding 95% confidence intervals.

The below change is incorporated into SAP amendment 2 as per clinical trial team (CTT)suggestion. This change do not alter the purpose or intent of the amendment. The aim of this memorandum is to clarify this sentence.

Protocol amendment version 03:

- Section 12.2: Demographic and other baseline disease characteristics will be listed and summarized descriptively for all subjects in the FAS as well as for those subjects in FAS who have completed the treatment.
 - *Demographic and other baseline disease characteristics will be listed and summarized descriptively for all subjects in the FAS.*

The below changes are incorporated into SAP amendment 4 as per clinical trial team (CTT) suggestion. These changes do not alter the purpose or intent of the amendment. The aim of this memorandum is to clarify these sentences.

Protocol amendment version 03:

- Section 12.4.4 (Supportive analyses): Percent reduction from baseline in priapic events will also be assessed by Week 52.
 - *Percent reduction from baseline in priapic events will also be assessed by Week 52. Assuming uniformity in the occurrence of priapic events before exposure to crizanlizumab treatment, baseline will be adjusted for 52 weeks for analysis purpose.*
- Section 12.5.1: The percent reduction from baseline in acute priapic events by 26 and 52 weeks of treatment.
 - *The percent reduction from baseline in acute priapic events (defined as an unwanted, painful erection that lasts more than 4 hours and need a visit to emergency room) by 26 and 52 weeks of treatment. Note that, this analysis will only be performed if an adequate number of subjects are present.*

5 Appendix

5.1 Imputation rules

5.1.1 Study drug

The following rule will be used for the imputation of the dose end date for a given study treatment component:

Scenario 1: If the dose end date is completely missing and there is no end of treatment (EOT) page and no death date, the subject is considered as on-going:

The subject should be treated as on-going and the cut-off date should be used as the dose end date.

Scenario 2: If the dose end date is completely or partially missing and the EOT page is available:

Case 1: The dose end date is completely missing, and the EOT completion date is complete, then this latter date should be used.

Case 2: Only Year(yyyy) of the dose end date is available and yyyy < the year of EOT date:

Use Dec31yyyy

Case 3: Only Year(yyyy) of the dose end date is available and yyyy = the year of EOT date:

Use EOT date

Case 4: Both Year(yyyy) and Month (mm) are available for dose end date, and yyyy = the year of EOT date and mm < the month of EOT date:

Use last day of the Month (mm)

All other cases should be considered as a data issue and the statistician should contact the data manager of the study.

After imputation, compare the imputed date with start date of treatment, if the imputed date is < start date of treatment:

Use the treatment start date

Subjects with missing start dates will be considered missing for all study treatment component related calculations and no imputation will be made. If start date is missing then end-date will not be imputed.

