### **Treatment phase**

Once eligibility criteria have been confirmed by Novartis via the eligibility checklist, the subject will receive investigational treatment.

Subjects will receive investigational treatment by IV infusion over 30 min on Week 1 Day 1, Week 3 Day 1, and then on Day 1 of every 4-week cycle.

Safety will be monitored as outlined in [Section 8](#). Subjects will receive investigational treatment for a maximum of 1 year (52 weeks) or until unacceptable toxicity, death, lost to follow-up or discontinued from the study treatment for any other reasons prior to 52 weeks.

[figure not shown]
Following the treatment discontinuation, subjects will perform an end of treatment (EOT) visit.

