#### 6.1.1 Investigational and control drugs

Crizanlizumab will be supplied in single use vials containing 10 mL at a concentration of 10 mg/mL for administration by IV infusion. Each study site will be supplied with study drug in packaging as described under investigational drugs section.

A unique medication number is printed on the study medication label.

On infusion day, the pharmacist or designated personnel will prepare individual doses of crizanlizumab for subjects on a milligram per kilogram basis in a 100 mL infusion bag in accordance with the Pharmacy Manual. Study drug will be administered over 30 minutes by IV infusion. Please refer to [Table 6-1](#) for dose and treatment schedule.

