2.1.1 General definitions

Study treatment: Study treatment refers to Crizanlizumab (SEG101) 5.0 mg/kg provided by IV infusion.

Study treatment start and end date: Study treatment start date is defined as the first date when a non-zero dose of study drug is administered and recorded on the Drug Administration Record (DAR) CRF page. Similarly, study drug end date is defined as the last date when a non-zero dose of study drug is administered and recorded on the DAR CRF page of the core study.

Baseline: Baseline period is defined as 12 weeks screening period prior to the first infusion of crizanlizumab 5 mg/kg at Week 1 Day 1.

- For the analysis purpose, in the tables and figures, baseline is considered from Day -91 to one day prior to dosing. Similarly, for "by week 26 analysis" from the first dose date to one day prior to Week 27 Day 1 visit date and for "by week 52 analysis" from the first dose date to one day prior to Week 53 Day 1 visit date will be considered.
- For subjects missing "Week 27 Day 1" visit or "Week 53 Day 1" visit, the scheduled visit day will be considered for cut-off.
- For listings, all available data will be considered.

For safety evaluations, the last available assessment on or before the date of start of study treatment is taken as "baseline" assessment. In case time of assessment and time of treatment start is captured, the last available assessment before the treatment start date/time is used for baseline.

For safety parameters (e.g. ECGs), where study requires multiple replicates per time point, the average of these measurements will be calculated for baseline (if not already available in the database).

In cases where multiple measurements meet the baseline definition, with no further flag or label that can identify the chronological order, then the following rule should be applied: If values are from central and local laboratories, the value from central assessment should be considered as baseline. If multiple values are from the same laboratory (local or central) or collected for ECGs or vital signs, then the last entry should be considered as baseline.

If subjects have no value as defined above, the baseline result will be missing.

Post baseline: Any measurements taken after baseline will be considered as post-baseline measurements.

Change from baseline: Post baseline value – baseline value

Percent change from baseline: (Post baseline value – baseline value) *100/ Baseline value;
(relative change from baseline).

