2.5.3 Handling of intercurrent events

The imputation of missing data caused by intercurrent events will be handled by defining the estimand framework.

The primary estimand is described by the following four attributes:

1. The target population comprises Sickle Cell Disease Patients with Priapism.
2. The primary variable is percent reduction from baseline period in priapic events (priapism defined as unwanted, or painful erection lasting at least 60 min self-reported) by 26 weeks.
3. Treatment of interest: investigational drug will be a crizanlizumab solution provided every 4 weeks with an additional loading dose 2 weeks after the first dosing.
4. The intercurrent events are the events occurring after enrollment that may impact the treatment effect. The intercurrent events of interest are listed below:
 - a. Treatment discontinuation
 - b. Initiation or discontinuation of HU/HC or l-Glutamine (or other therapies to treat SCD and or to prevent/reduce VOCs such as voxelotor and erythropoietin) or of prophylactic treatment for priapism
 - c. Intake of analgesic (including opioids) or ad hoc transfusions administered temporarily
5. The summary measure is the median percentage change from baseline period in priapic events (priapism defined as unwanted, or painful erection lasting at least 60 min self-reported) by 26 weeks.

Handling of the intercurrent events:

The approach of accounting for intercurrent events is as follows:

- **For the intercurrent events 4a:** Only data before study treatment discontinuation will be included. The data between treatment discontinuation and week 26 will be imputed using Poisson distribution (primary method to handle missing data as described in [Section 2.5.4](#)).
- **For the intercurrent events 4b:** Only data before initiation or discontinuation of HU/HC or L-Glutamine (or other therapies to treat SCD and or to prevent/reduce VOCs such as Voxelotor and erythropoietin) or of prophylactic treatment for priapism will be included. The data between initiation or discontinuation of therapies to treat SCD or of prophylactic treatment for priapism and week 26 will be imputed using Poisson distribution (primary method to handle missing data as described in [Section 2.5.4](#)).
- **For the intercurrent events 4c:** Data after intake of analgesic (including opioids) or ad hoc transfusions administered temporarily will be included (treatment policy strategy).

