2.6.2 Statistical hypothesis, model, and method of analysis

Similar analyses on percent reduction in acute priapic events for subjects from full analysis set will be conducted, as done for primary endpoint.

Annualized rates will be calculated for the secondary endpoints.

The annualized rate of events is defined as the total number of events for a subject occurring from the date of initial infusion to the last contact date of the Treatment Phase of the study x 365.25 divided by the number of days during that same time period. This calculation accounts for early dropouts or lost to follow-up by extrapolating the priapism events rate of every subject to 1 year.

Annualized events rate = Total number of events x 365.25 / (end date – treatment start date +1), where end date is defined as the minimum of (last dose date until treatment discontinuation + 27 days, date of initiation or discontinuation of HU/HC or L-glutamine - or other therapies to treat SCD and or to prevent/reduce VOCs such as voxelotor and erythropoietin, cut-off date).

Descriptive summary statistics including n, mean, standard deviation (SD), lower quartile (Q1), median, upper quartile (Q3), minimum, and maximum will be presented for the annualized rate of events and number of priapic events at Baseline, by Week 26 and by Week 52 .

The change from baseline in rates of events at Week 26 (i.e. evaluation at Week 27, Day 1) and Week 52 (i.e. evaluation at Week 53, Day 1) will be summarized by n, mean, median, standard deviation (SD), lower quartile (Q1), median, upper quartile (Q3), and minimum and maximum.

Graphical representation of annualized rates, through box plots or bar graphs or swimmer plot, as appropriate, will also be performed.

The Annualized Rates of Events at Week 26 (i.e. evaluation at Week 27, Day 1) and Week 52 (i.e. evaluation at Week 53, Day 1) will be summarized by n, mean, standard deviation (SD), lower quartile (Q1), median, upper quartile (Q3), standard deviation and minimum and maximum.

Additionally, cumulative number of acute priapic events, uncomplicated and complicated VOC events will also be summarized over time (like 0-12 weeks, 0-26 weeks, 0-40 weeks and 0-52 weeks).

Subgroup analyses displaying annualized rate, for complicated and uncomplicated VOC events will be performed based on use of hydroxyurea versus no use of hydroxyurea by 26 weeks and 52 weeks.

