5.1.3.3 Other imputations

Table 5-5 Imputation of start dates assessments (laboratory, ECG, vital signs)

Missing Element	Rule
day, month, and year	
• No imputation will be done for completely missing dates
day, month	
• If available year = year of study treatment start date then
◦ If stop date contains a full date and stop date is earlier than study treatment start date then set start date = 01JanYYYY
◦ Else set start date = study treatment start date.• If available year > year of study treatment start date then 01JanYYYY• If available year < year of study treatment start date then 01JulYYYY
day	
• If available month and year = month and year of study treatment start date then
◦ If stop date contains a full date and stop date is earlier than study treatment start date then set start date= 01MONYYYY
◦ Else set start date = study treatment start date.• If available month and year > month and year of study treatment start date then 01MONYYYY• If available month and year < month year of study treatment start date then 15MONYYYY

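### Three date-imputation rules in SAP 5.1 do not fit this trial and give wrong dates when they are triggered, probably in few records

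*SAP*

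**What the plan says.** **Study drug.** SAP 5.1.1 covers a dose record whose end date is missing. If an EOT page exists: "The dose end date is completely missing, and the EOT completion date is complete, then this latter date should be used". If there is no EOT page and no death: "The subject should be treated as on-going and the cut-off date should be used as the dose end date". SAP 2.1.1 defines the quantity differently: "study drug end date is defined as the last date when a non-zero dose of study drug is administered". Protocol 6.1.1 describes the dose: "Study drug will be administered over 30 minutes by IV infusion".

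**Assessments.** Table 5-5 (SAP 5.1.3.3) covers partial laboratory, ECG and vital-sign dates. It applies when only the year is known and it is the treatment-start year, or when only the day is missing and the month is the treatment-start month. Unless a full stop date lies before treatment start, the instruction is: "Else set start date = study treatment start date". SAP 2.1.1 takes the last assessment up to and including the treatment-start date as the safety baseline, or the last one before the treatment-start time where times are captured. The visit-window text in the same section gives laboratory baseline a window of Day -28 to Day -1.

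**Medications.** Table 5-3 (SAP 5.1.3) applies the same rule to medication start dates. SAP 2.5.3, event 4b, then limits the primary data: "Only data before initiation or discontinuation of HU/HC or L-Glutamine" (and other sickle cell therapies, or priapism prophylaxis) are used, and the remainder to week 26 is imputed. SAP 2.6.2 ends the annualized-rate period at the earliest of several dates, one of them being the "date of initiation or discontinuation of HU/HC or L-glutamine - or other therapies to treat SCD".

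**The concern.** The study-drug rule reads as if treatment ran continuously up to EOT. Here doses are separate infusions, each starting and ending on the same day, and EOT is planned two weeks after the last one (Protocol 8). The rule therefore contradicts the SAP's own definition of drug end. Its other branch relies on a cut-off date, and SAP 2.1 says the final analysis has none.

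Table 5-5 tests a stop date that a point assessment does not normally have, so the fallback to Day 1 applies. A sample taken after dosing can then land on the one day where the baseline definition may accept it.

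Table 5-3 is harmless in the medication tables, because an ongoing drug counts as concomitant whether it began before Day 1 or on it. It is not harmless if the same imputed date decides whether background therapy was started on study. That decision determines which observed priapism counts enter the primary analysis, in a trial planned for 34 evaluable subjects.

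**Working it through.** **1. Infusion end date**

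SAP Table 2-1 gives scheduled day d = (k - 1) × 7 + 1. Week 51 (last infusion): 50 × 7 + 1 = 351. Week 53 (EOT): 52 × 7 + 1 = 365. Both match the table, and the gap is 14 days.

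SAP 2.4.1 gives exposure in weeks as (last treatment day + 27 - 1 + 1)/7, before any cap at death or cut-off.

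- True last infusion, Day 351: (351 + 27)/7 = 54.0 weeks.
- EOT on Day 365 used instead: (365 + 27)/7 = 56.0 weeks.
- EOT at the ±7-day limits: (358 + 27)/7 = 55.0 and (372 + 27)/7 = 57.0 weeks.

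The on-treatment window is last dose + 105 days: 351 + 105 = 456, against 365 + 105 = 470. For a subject who continues on commercial supply the window ends at EOT, so this shift does not arise.

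Doses fall at Weeks 1 and 3 and then every 4 weeks from 7 to 51: 2 + 12 = 14 infusions, or 14 × 5 = 70 mg/kg. Dose intensity is 70/54 × 4 = 5.19 against 70/56 × 4 = 5.00 mg/kg per 28 days. Relative dose intensity is essentially unchanged, because the same duration divides both actual and planned dose and no infusion is scheduled between Day 351 and Day 365.

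**2. Assessment date** (illustrative first infusion 1 March 2021)

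- Week 3 sample of 15 March recorded as March 2021: becomes 1 March, Day 1.
- Week 27 sample of 30 August recorded as 2021: becomes 1 March, Day 1.
- Week 7 sample of 12 April recorded as April 2021: becomes 1 April, Day 32, which stays in the Week 7 window (Day 30-57).

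The fault is thus confined to year-only dates in the treatment-start year and day-missing dates in the treatment-start month. Where times are not captured, the 2.1.1 baseline definition admits the first two values. The visit windows in the same section do not: Day 1 falls in Week 1, and laboratory baseline stops at Day -1.

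**3. Background therapy**

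Inclusion criteria 6 and 7 require at least 14 weeks of use before screening. With 12 weeks of screening that is 26 weeks, or 182 days, before Day 1 (ignoring visit windows).

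- Illustrative first infusion 15 September 2021: the latest eligible hydroxyurea start is 17 March 2021. An ongoing record dated only 2021 becomes 15 September, Day 1, which eligibility rules out.
- For therapy start and first infusion to share a calendar year, the first infusion must fall on or after 2 July in a 365-day year: 365 - 182 = 183 of 365 dates.
- A record dated only 2020 becomes 1 July 2020 and does no harm. A record missing only the day does no harm either, because an eligible user's start month precedes the treatment-start month.

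If the imputed date fed event 4b, all 26 weeks of observed counts would be dropped and replaced by Poisson draws. If it fed 2.6.2, the period would be Day 1 - Day 1 + 1 = 1 day instead of 182.

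**The case against.** The case on the other side is that these are fallbacks that will rarely operate. Infusions are supervised at site (Protocol 6.6.1) and missing values are queried (Protocol 11.2). The ordinary shift in part 1 is two weeks in a descriptive summary. In part 2, the windows keep a Day 1 value out of the laboratory baseline in by-visit tables, and ECGs are scheduled only at screening and end of treatment. In part 3, nothing in the SAP says event 4b uses imputed dates. All of this stands as a limit on frequency and reach. It does not make the resulting dates correct, and it leaves two statements about baseline in SAP 2.1.1 unreconciled.

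A reader might infer more, without support from the documents:

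- **A hugely inflated annualized rate**, from a 26-week count over one day. SAP 2.6.2 counts events and days over the same period, so the count would be Day 1 events only. The result would be an uninformative one-day rate, not a 26-week count multiplied up.
- **Prophylaxis shortening the rate period.** The 2.6.2 list names hydroxyurea, L-glutamine and other SCD/VOC therapies. Priapism prophylaxis appears only in event 4b.
- **A much larger exposure error**, from pairing a Day 351 last infusion with the Day 447 upper limit for EOT. The documents do not say these belong to one subject. With EOT planned two weeks after the last infusion, delayed dosing explains a late EOT equally well.
- **Real therapy stops hidden by Table 5-4**, which moves year-only stop dates late. Protocol 6.2.1.1 and 6.2.1.2 require on-study changes to hydroxyurea, L-glutamine, voxelotor and prophylaxis to be notified, so a better date should exist.

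**Conclusion.** The point holds in a limited form. Each of the three rules, applied as written, gives a date that conflicts with this trial's dosing, baseline definition or eligibility criteria.

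The quantified effect is in part 1: 56.0 instead of 54.0 weeks of exposure for a completer with an on-time EOT, and an on-treatment window 14 days too long for subjects not moving to commercial supply. Part 2 can put a post-dose value into baseline only where times are not captured and the 2.1.1 baseline definition is followed rather than the visit windows. Part 3 could reach the primary endpoint, but only if imputed dates feed event 4b. It also needs a year-only record of therapy that began in the treatment-start year and a first infusion from about July.

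The documents do not say how many partial dates there are; I assume few. They do not show that the primary result is affected, and the calendar dates in the working are illustrations.

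**What to change.** - **5.1.1:** set a missing infusion end date to that infusion's start date, and drop the EOT and cut-off substitutions for study drug.
- **Table 5-5:** use the recorded visit date for a partly dated assessment. State that an imputed assessment date never defines baseline, and reconcile the up-to-and-including-Day-1 baseline definition in 2.1.1 with the Day -28 to Day -1 laboratory window.
- **5.1.3:** state that imputed medication dates are not used for event 4b or for the 2.6.2 end date. Treat therapy accepted under inclusion criteria 6 and 7 as pre-existing, and date on-study changes from the query response or the notification to the monitor.

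The cost is a few sentences in the SAP and a small number of data queries, with no new data collection. It should be done before database lock.
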